2. PEDI-CAT (ASD)

Stephen M. Haley PhD, PT, FAPTA Wendy J. Coster PhD, OTR/L, FAOTA Helene M. Dumas PT, MS Maria A. Fragala-Pinkham PT, DPT, MS Richard Moed MPA

The PEDI-CAT (ASD) is a module of the PEDI-CAT that has been validated for the population of children and adolescents with ASD. Research also supports the test-retest reliability of the PEDI-CAT (ASD) with ICC values indicated excellent score reliability over the test–retest period for all PEDI-CAT (ASD) domains: The Daily Activities ICC value was 0.92, the Social/Cognitive value was 0.86, and the Responsibility value was 0.90. This module includes additional directions to help parents select an appropriate rating given the unique characteristics of children with autism. In addition, the scores in the Social/Cognitive domain are based on the unique patterns of children and youth with autism, but are expressed on the same metric as the original PEDI-CAT (Kramer, Liljenquist & Coster 2016) The PEDI-CAT is designed for use with children and youth (birth through 20 years of age) with a variety of physical and/or behavioral conditions (<https://www.pedicat.com/>).

3. Sensory Processing Measure™ (SPM™)

L. [name], OTR/L, FAOTA, Cheryl Ecker, MA, OTR/L, Diana A. Henry, M.S., OTR/L, FAOTA, et al

The *Sensory Processing Measure* (SPM) is a norm-referenced assessment of sensory integration/sensory processing that gathers information about a child’s behavior, coordination, and participation at home, in the community, and/or at school. For the purposes of the study the Home Form will be utilized. Per test manual, the SPM has good test-retest reliability ($r \geq .94$ on all scales). Separate scores are provided for social participation, five sensory systems, and motor planning in the home. Additional scores may be obtained for six different school settings, including art class, music class, physical education class, the playground, the cafeteria, and the school bus. *Sensory Processing Measure* (SPM) can be used with 5- to 12-year-old children, including 5-year-olds who have already started kindergarten (Parkham, Kuhaneck, Henry & Glennon, 2007).

4. Autism Treatment Evaluation Checklist (ATEC)

[name], [name]

The ATEC is a 77-item assessment tool developed at the Autism Research Institute. It was developed to provide a free, easily accessible, and valid tool to measure changes in ASD symptoms over time. The ATEC can be completed by parents, teachers, or others who see the individual’s behavior on a regular basis. The ATEC consists of four subtest scales: Speech/Language/Communication, Sociability, Sensory/Cognitive Awareness, and Health/Physical Behavior. The four subscale scores are used to calculate a total score (77 items – score range 0 to 180). A lower score indicates less severe symptoms of ASD and a higher score correlates with more severe symptoms of ASD. Baseline

Modification / Update, MOD006-STU-2019-1698, [name], 4/12/2025

scores can be compared with post-intervention scores to assist with determining intervention efficacy. Per data collected by the Autism Research Institute, Pearson split-half coefficients were calculated to examine the internal consistency. Subscale coefficients ranged from .82 - .92 and the total score coefficient was .94, indicating high internal consistency (Rimland & Edelson, 1999). Research shows the ATEC is highly correlated ($\rho = .71, p < .0001$) with the Childhood Autism Rating Scale (CARS), which is a widely used and well validated measure used to identify ASD (Geier et al., 2013), and there is some preliminary evidence that supports the use of the ATEC to monitor progress of children with ASD over time (Magiati et al., 2011).

The caregivers will be given a choice between a base schedule which includes two 15 minute sessions with at least 30 minutes in between sessions of listening per day for 5 consecutive days and two days off or a condensed schedule of one 30-minute session of listening per day for 5 consecutive days and two days off. A handout for the selected listening schedule will be given during the initial session.

Testing – using the same 4 questionnaire based assessments- will be completed at the 41st week after treatment these assessments, and then again after 3 months of no treatment. These visits are expected to take approximately 60 – 90 minutes, and the final visit may be completed in-person or using a hospital approved virtual platform. Between testing sessions for both groups, caregivers and investigators will set up three phone calls or hospital approved virtual platform meetings at approximately 10 week intervals to check in and answer questions.

The total time spent face-to-face with a study investigator is expected to be about 2.5-5 hours per participant.

5. Sub-Study Procedures:

This project does not have a sub-study.

6. Criteria for Inclusion of Subjects:

Children will be eligible to participate in this study if they are:

Between the ages of 5 and 10 years old

Diagnosis of autism spectrum disorder

Auditory SOR defined by “Some Problems or Definite Dysfunction” on the Hearing section on the Sensory Processing Measure Home Form.

Caregiver must be available to supervise listening sessions at home

English Speaking

7. Criteria for Exclusion of Subjects:

Children will be excluded from the study if they are:

Modification / Update, MOD006-STU-2019-1698, [name], 4/12/2025

Diagnosed with seizure disorder
Hearing impairments
Cerebral palsy
Fragile X syndrome or genetic disease
Previous use of a listening based system
Non-English speakers

8. Sources of Research Material:

All the data described here is being collected specifically for research purposes.

Parents/legal guardians of the study participants will provide general information about their child by completing a demographic form. Information requested will include: the child's full legal name, age, gender, co-morbidities, list of medications being taken, physician's name, list of previous and current therapies and contact information prior to use of the listening-based program. The research data collected from the assessments Adaptive Behavioral Assessment Systems (ABAS-3), Pediatric Evaluation of Disability Inventory (PEDI-CAT-ASD) and the Sensory Processing Measure (SPM), and the Autism Treatment Evaluation Checklist (ATEC) will be the source of research data being collected.

9. Recruitment Methods and Consenting Process:

Potential participants will be given flyers that will be provided by rehabilitation services at Children's Health Rehabilitation Services at all locations either by a therapist or by the front desk. At the Center for Autism and Developmental Delays (CADD) clinic by flyers will be available in lobby area and/or physicians will give flyer to individual patients. They can contact the researchers via phone or email after learning of the study. If a therapist who is not a member of the study identifies a potential participant and learns of the parent's interest in the study, the therapist may inform the study team who would then contact the parent to discuss participation in the study. The research team would contact the parent only if the therapist indicates that the parent is agreeable to being contacted by the researchers. If there is a lack of potential participants after three months, flyers will be distributed outside of the Children's Health System. With administrative permission flyers to be given to local pediatricians' offices, private schools for children with special needs, and pediatric therapy private practices. The researchers will also register the study in ClinicalTrials.gov.

Interested subjects can contact the research team via phone or email or vice versa so the team can answer any questions parents may have regarding the study. If they are interested in moving forward after that, a member of the research team and the parent will speak on the phone to complete an eligibility screening, including 8 questions on auditory SOR (Hearing Section) on the Sensory Processing Measure- Home Form to determine if the child meets the criteria for auditory SOR for this study. On the Sensory Processing Measure (SPM), the Hearing section score must indicate "Some Problems" or "Definite Dysfunction" to be enrolled in this study. After parents have their questions answered they will be asked whether they are

Modification / Update, MOD006-STU-2019-1698, [name], 4/12/2025

interested in having their child enrolled in the study.. If the child is eligible and the if the parents agree to have their child participate, a meeting at a Children's Health Specialty Center will be set. During this meeting, the study principal or co-investigator will complete the consent interview with the family. If the family agrees to participate after completing the consent interview and signs the informed consent form, the meeting will continue and the initial visit will begin.

10. Potential Risks:

This study poses no more than minimal risk to participants and their families. The questionnaire-based assessments used in the three data collection sessions are often administered by occupational therapists in pediatric rehabilitation settings, among other places, and are not known to cause any harm. Any adverse physical or psychological harm to study participants during the administration of Listening Program® Spectrum music with Waves™ (bone conduction) headphones is unlikely. The parent will have instructions on safe and appropriate usage of the Listening Program® at home, including recommendation to supervise their child during use and parents be in the line of sight of their child, how to don the headphones correctly (correct ear placement will be noted on the headphones), and how to accommodate fit of headphones for small children (e.g., using a headband or rolled up bandana to keep them in place). However, if the child is unattended while doing the Listening Program, possible risks include: chewing or otherwise tampering with the cord, moving the plug from the correct placement in the amplifier, raising the volume to an uncomfortable level, or discomfort due to headphones slipping out of place or placed backwards on the child's head. There may also be the risk of strangulation from the cord if the child is left unsupervised.

11. Subject Safety and Data Monitoring

During the three data collection sessions study participants will be asked to come to a Children's Health Specialty Center to fill out the 4 questionnaire-based assessments with the principal investigator or co-investigator. If preferred, parents can complete the final data collection session using a hospital approved virtual platform.

Given the nature of this study a Data Safety Monitoring Plan is not needed.

12. Procedures to Maintain Confidentiality:

Study participants have been assigned a code that has been used on all data collection forms. The code will be known by the PI and co-investigators. The de-identified test forms (data collection forms), research binder and demographic page will be stored electronically in a password protected drive. Paper copies of consent forms will be kept in a locked file cabinet in the Rehabilitation Services office at Children's Health Richardson Specialty Center. The information collected by the investigator and co-investigators will be retained by Children's Health for 10 years after completion of the study according to the data retention policy for research. De-identified data including demographics and results of questionnaires (or any other data) will be shared with Advanced Brain Technologies.

We do not intend to apply to NIMH for a Certificate of Confidentiality.

Modification / Update, MOD006-STU-2019-1698, [name], 4/12/2025

13. Potential Benefits:

The findings from this study will begin to fill in a gap of knowledge regarding the utilization of listening-based programs for the treatment of auditory (SOR) in children with autism. This study will also serve as a catalyst for other studies investigating the potential benefits of listening based programs.

The parents, legal guardians, and children who participate in the study will be provided with an oral report using lay terminology that summarizes changes in the questionnaires following the study, which they may consider a potential benefit to participation in the study. The patients will be provided with listening-based therapy at no cost. Aside from this there is no other direct benefit to participants.

14. Biostatistics:

Sample Size and Power: This is a pilot study. Each patient is measured at 3 phases: baseline, intervention and post intervention. The total sample size is of 8 patients. This sample size is similar to the sample of 7 patients in the pilot study reported by [name], OTR, [name], OTR, and [name], 2015.

Statistical Analysis Plan: Descriptive analyses will be performed for the demographic and prognostic characteristics of the patients. Categorical variables will be reported with frequencies and proportions; continuous variables will be reported with means and standard deviations. The primary outcome is the ABAS-3 general adaptive composite score. The raw scores will be summarized in a box-and-whisker plot illustrating score distributions at baseline, at intervention and post intervention. Shapiro-Wilk and Kolmogorov Smirnov tests will be used to test whether the composite score follows normal distribution. If the composite score deviates significantly from normal distribution, transformation will be applied. Piecewise linear mixed-effects model could be used to model the score change over the 3 stages in the study. The statistical analyses will be performed with SAS version 9.4 (SAS Institute, Inc., Cary, NC).

References

Advanced Brain Technologies 6/2010 Certification course

Allen, S. (Dec. 2008) ABT Bone Conduction System Provider Reference Document

American Psychiatric Association: Diagnostic and Statistical Manual of Mental Disorders: Diagnostic and Statistical Manual of Mental Disorders, Fifth Edition. Arlington, VA: American Psychiatric Association, 2013.

Modification / Update, MOD006-STU-2019-1698, [name], 4/12/2025

- Berard, G. (1993). *Hearing and Behavior*. CT: Keats Publishing, Hearing equals behavior (pp 15-37)
- Harrison, P.L. & Oakland, T. (2015). *Adaptive Behavior Assessment System, Third Edition* [Manual], Torrance, CA: Western Psychological Services.
- <https://integratedlistening.com/about-ils/>

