The most common sensory perceptual abnormality is auditory sensory over-responsivity (SOR). SOR is characterized by a quicker, more intense, and/or longer duration response to sensation than those with typical sensory responsivity (Miller et al., 2007). Children with ASD can have abnormal and often severe behavioral reactions to a variety of sounds in their everyday environment (Doman & Lucker, 2015). The fight or flight response elicited by auditory SOR increases maladaptive behavioral responses in a variety of environments and negatively impacting adaptive living skills. Adaptive life skills are everyday skills needed to function and meet the demands of one's environment, including independent self-care and social interaction.

Modification / Update, MOD006-STU-2019-1698, [name], 4/12/2025

Given the increased prevalence of ASD and the heightened awareness of sensory over- and under-responsivity (SOR) (SUR), particularly to auditory input, as a component of ASD, there is a growing need for evidence-based treatments to relieve discomfort and lessen behavioral reactions to a variety of every day environmental sounds to support improved adaptive life skills.

The objective of this study is to investigate changes in adaptive life skills and behavioral responses in children with ASD using Advanced Brain Technology's Listening Program® Spectrum music utilizing Waves™ (bone conduction) headphones.

The information obtained will contribute to a more comprehensive and evidence-based approach to the treatment of auditory SOR in children with ASD. It is expected that reducing auditory SOR will improve adaptive living skills at home, school, and in the community.

2. Background

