The study will use a nonconcurrent AB multiple baseline design, with A representing the baseline phase and B representing the intervention phase with a postintervention non-treatment phase. At baseline (A), demographic information will be collected and the following outcome measures will be completed: the Pediatric Evaluation of Disability Inventory Computer Adaptive Test with ASD Scales (PEDI CAT(ASD)), Sensory Processing Measure (SPM) home form, the Adaptive Behavioral Assessment System 3rd Edition ABAS-3 and Autism Treatment Evaluation Checklist (ATEC). During the intervention (B) phase, parents of participants in the treatment group will be educated by the investigators on use of The Listening Program at home, and then participants in this group will receive treatment at home utilizing The Listening Program for 40 weeks. Testing, using the same 4 outcome measures, will be completed at the 41st week after use, and then again after 3 months of no treatment. Between testing sessions, caregivers and investigators will set up three phone or hospital-approved virtual platform meetings at approximately 10 week intervals to check in and answer questions. The study is expected to run until the target number of 5 to 8 participants are enrolled.

4. Study Procedures:

Methodology: The caregivers of the children will meet with the principal or co-investigator for a 90-minute to 2-hour meeting. The meeting will include education on auditory SOR and the usage of the listening program and utilization of the wave bone conduction headphones for. All caregiver questions will be answered with caregivers verbalizing understanding of the research process, auditory SOR and equipment use. During this initial session, 4 questionnaire-based assessments, demographic information sheet and Consent to Participate in Research Form will be completed. A handout will be provided to the parent or caregiver which will include proper care, use and return of the "Waves"™ headphones and amplifier along with instructions to utilize the online listening system. Parents and caregivers will have the opportunity to ask questions and receive clarification about the study prior to signing the consent form.

The questionnaires based assessments include:

1. Adaptive Behavior Assessment System, Third Edition (ABAS-3)

[name], [name]

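### Does Section 14 need a planned analysis for the three questionnaires other than the ABAS-3?

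*Combined protocol and SAP*

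**What the plan says.** The opening section, before Section 2, sets a two-part aim: "The objective of this study is to investigate changes in adaptive life skills and behavioral responses in children with ASD". It adds that "The information obtained will contribute to a more comprehensive and evidence-based approach to the treatment of auditory SOR in children with ASD", and it expects less auditory sensory over-responsivity (SOR) to bring better adaptive skills.

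Section 3 lists four questionnaires at baseline: PEDI-CAT (ASD), SPM Home Form, ABAS-3 and ATEC. It continues: "Testing, using the same 4 outcome measures, will be completed at the 41st week after use", with a third round three months after treatment stops. Section 8 names all four as the research data.

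Section 14 then states: "The primary outcome is the ABAS-3 general adaptive composite score". The box plot, normality tests, possible transformation and optional piecewise mixed model all follow from that score. The other three instruments are not mentioned there, and no section names a secondary outcome.

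Section 4 describes what those three instruments yield, without choosing among their scores:

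- SPM: "Separate scores are provided for social participation, five sensory systems, and motor planning in the home".
- ATEC: "The four subscale scores are used to calculate a total score", and baseline "scores can be compared with post-intervention scores to assist with determining intervention efficacy".
- PEDI-CAT (ASD): test-retest figures for three domains, "The Daily Activities ICC value was 0.92, the Social/Cognitive value was 0.86, and the Responsibility value was 0.90".

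The SPM Hearing section has a stated role only at entry (Sections 6 and 9).

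**The concern.** A reader who follows Section 14 to the letter gets an answer on adaptive skills and none on behavioral responses or on auditory SOR. SOR is the treatment target and defines who may enter, so the first link in the study's reasoning (less SOR, hence better adaptive skills) has no planned estimate.

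The second worry is selective reporting. Section 4 describes seven SPM scores, five ATEC scores (four subscales and a total) and three PEDI-CAT (ASD) domains. If no score is named in advance, one that happened to improve could be presented as the result. Section 11 has investigators present while parents complete the forms, so scores could be seen as they accrue. Section 13 promises families a summary of questionnaire changes, so changes will be worked out in any case.

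**Working it through.** **1. Count.** These figures come from the opening section and Sections 3, 8 and 14.

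| Item | Total | With an analysis in Section 14 |
|---|---|---|
| Instruments called outcome measures | 4 | 1 (ABAS-3) |
| Parts of the objective | 2 | 1 (adaptive life skills) |
| Analyses of change in auditory SOR | – | 0 |

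**2. Does other text close the gap?** No.
- Section 14's mention of raw scores comes straight after the primary-outcome sentence and just before a reference to the composite, so it means the ABAS-3.
- The descriptive analyses in Section 14 cover demographic and prognostic characteristics.
- The ATEC remark in Section 4 says what the tool allows.
- The report to families in Section 13 is a lay summary.

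**3. Does the gap alter anything the plan does produce?** No. The ABAS-3 composite is identified as primary. Section 14 states no significance level and no success rule that combines instruments. Adding or omitting analyses of the other three leaves the ABAS-3 estimate as it was.

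**4. How open is the choice left to the analyst?**
- *Auditory SOR.* Sections 6 and 9 define it by the SPM Hearing section, so there is one natural score.
- *Behavioral responses.* The opening section speaks of behavioral reactions in connection with everyday sounds. On that reading the nearest collected score is again SPM Hearing. Nothing links the term to the ATEC total, which includes speech and physical health.
- *Contrasts.* Three visits give three pairs: baseline to week 41, baseline to follow-up, and week 41 to follow-up. All three can be shown.
- *Baseline.* Sections 4 and 9 put the telephone screen before the initial session, at which all four questionnaires are completed. A baseline separate from the screening score is therefore already planned, and regression to the mean from selection at screening should fall mainly between screen and baseline.

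**5. What would a written-in analysis deliver?** There is no sample-size calculation to reproduce: Section 14 gives 8 patients by analogy with an earlier pilot of 7, and Section 3 gives 5 to 8. The half-width of a 95% t-interval for mean within-child change, in standard deviations (SD) of change, is t(0.975, n−1)/√n:

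- n = 8: 2.365/2.828 = 0.84
- n = 5: 2.776/2.236 = 1.24

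Naming the score in advance does not narrow these intervals. Adding formal tests would bring a multiplicity problem of its own. With one test per instrument at an assumed two-sided 0.05, and independence assumed, the chance of at least one false positive is 1 − 0.95⁴ = 18.5%. The added analyses would have to be labelled exploratory or adjusted, and exploratory is how data of this kind are read already.

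**The case for a change.** The strongest case for a change is that one short paragraph, with no new data, would cover half the objective and the treatment target. It would also let readers tell a planned result from a chosen one. Questionnaire results go to the company that developed the program (Sections 2 and 12), which sharpens the point.

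The size of the selection problem can be illustrated. Suppose any of the five ATEC scores could be picked, there is no true change, n = 8, and correlations between scores are assumed to lie between 0.8 and 0.3. Simulation then puts the chance that at least one 95% interval favours improvement at 6.2% to 9.5%, against 2.5% for one named score.

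Part of this stands. The omission is not explained away by calling the study a pilot, and any strong claim resting on one of these instruments could not be called prespecified.

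The rest is weaker. The simulated rates need correlations that the documents do not give and a success rule that the plan does not contain. They also presume a free choice of score, whereas the protocol's wording leans towards SPM Hearing. Widening the pool to PEDI-CAT (ASD) would bring in domains such as daily activities, which look like adaptive skills and so belong to the other half of the objective. Finally, Section 12 says in the past tense that codes have been assigned and used on the forms. If scores have already been seen, a paragraph added now would make reporting more transparent but would not make the choice prespecified.

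**Conclusion.** The gap is genuine: three of four instruments, and one of two parts of the objective, have no planned analysis. It is missing detail that an analyst would fill sensibly, by tabulating and plotting within-child changes on all four questionnaires and treating everything except the ABAS-3 composite as exploratory. The effect on the planned primary result is nil. With 5 to 8 uncontrolled children and half-widths of 1.24 to 0.84 SD of change, a more formal plan would add little information, and which score should stand for behavioral responses is debatable.

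This rests on two assumptions: that all three instruments are reported, not one selected result, and that behavioral responses means reactions to sound. If a report made a confirmatory claim on a single SPM, ATEC or PEDI-CAT (ASD) score, the concern would count against that claim. It does not require a change to the plan.
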